### **3.5.3. Exploratory Endpoints**

The mechanisms of GC resistance will be explored (Appendix F) by dividing subjects into response categories for the following assessment in all subjects:

- a) GI absorption of prednisone by evaluation of plasma levels of prednisone/prednisolone
- b) intracellular cytokine profiles in lymphocytes using multiparameter flow cytometry
- c) RNA expression profiles by microarray profiling of whole blood
- d) GR isoform assessments: GR isoforms will be assessed on all subjects using RT-PCR to understand relationship between responsiveness and predominant isoforms
- e) Proteomics: A collaboration with [name] (Assistant Professor, [name]) has been initiated using samples from the screening protocol for eosinophilia (94-I-0079). If preliminary findings are promising, coded samples, without personal identifying information, from 12-I-0026 will be sent to him for further proteomic evaluation of steroid responsiveness.

Not all studies will be performed for each subject due to time or sample constraints, although efforts will be made to proceed with exploratory investigations in a uniform manner. Additionally, investigations not outlined above may be performed based on preliminary findings and collaborations with other investigators in the field of GC responsiveness.

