# 6. Analysis Plan

## 6.1. Description of the Analyses

The primary objective of this study is to develop a model to predict GC responsiveness (see section 2) using the percent change in the eosinophil count at 4 or 24 hours following steroid challenge (ie, ERR). GC responsiveness is defined as the dose required to control disease manifestations and eosinophilia. Since this response is necessarily subject to many factors including physician expert opinion, it is important that the PI and Accountable Physician be blinded to the predictor variables. In order not

to compromise patient care, the 24 hour post-challenge CBC with differential will be assessed by an independent physician ([name] or her designee) who will decide whether un-blinding is necessary for patient safety.

To allow for flexibility in building the predictive model, we will first try the class of linear models on the GC responsiveness and pick the best model in terms of a small sample adjusted Akaike Information Criterion(16). If the fit of that model is not good (for example, the errors look far from normal), then transformations on the GC responsiveness may be tried. If none of those models have good fit, then we will consider a cumulative logit model where we partition the GC responsiveness into 3 ordered categories: steroid responsive (<15 mg of prednisone or equivalent alternate corticosteroid daily), moderately responsive (requiring between 16-40 mg of prednisone or equivalent), or resistant (>41 mg of prednisone required daily with or without a response).

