## 6.2. Sample Size Justification

The sample size of this study is practically limited by the number of subjects available for study. Currently, about 30-35 new hypereosinophilic subjects per year are seen at the NIH and enrolled on protocol 94-I-0079, of which approximately 10% would meet inclusion criteria for this protocol. Consequently, we expect that we can enroll 30-40 subjects in this study over a 13-year period.

To show that this number of subjects is not unreasonably small, we calculate the sample size for a Spearman's correlation coefficient. If true correlation is 0.5 between a predictor variable (ERR at 4 or 24 hours) and the GC responsiveness (see Description of the Study, Section 3.1), the total number of subjects needed to show that the correlation is different from zero at the two-sided 0.05 level with 80% power is about 32 subjects. We calculated this by simulating 10,000 data sets of 32 bivariate random normal variables with correlation 0.5 and seeing that the Spearman coefficient is significantly different from zero 79.5% of the time. This is similar to the usual sample size calculation for Pearson's correlation(17) or (18) that gives a sample size of 29 for the same situation.

Because the predictor and outcome variables are both continuous, if the true change in the dependent variables is 0.5 standard deviations per 1 standard deviation change in the independent variable, a clinically important measurement of association between response to a steroid challenge and final required dose of GC will be possible.

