## 6.3. Final Analysis Plan

### 1. Study Endpoints:

- Primary: GC responsiveness.
  - Definition: See primary endpoint for definition of GC responsiveness.
  - Validity and Reliability: This is a rare disease, and standard care for this disease is still being developed. There is no standard endpoint, and this endpoint has not been used before. One of the purposes of this study is to see if this endpoint can be reliably predicted. The endpoint has face validity because the dose that controls eosinophil concentration is useful for determining the extent of a subject's disease and their responsiveness to steroid therapy. We will first try and predict GC responsiveness as described in section "Description of the Analyses" (Section 6.1), but may also try to predict the categorization of the GC responsiveness into 3 ordered categories described in section "Description of the Analyses".
  - Predictor Variables: All predictor variables will be measured in the first 24 hours after initial dose, and will be blinded to the PI and Accountable Physician. These variables will be used to predict the GC responsiveness:

percent change in eosinophil count from baseline to 4 and 24 hours and steroid absorption.

- Secondary:
    - Classification of subjects by GC response for assessment of clinical factors associated with GC responsiveness (including HES variant, pattern of organ involvement and laboratory parameters)
  - Exploratory
    - Exploratory analyses of potential mechanisms and in vitro correlates of GC resistance, including impaired steroid absorption, cell surface markers on lymphocytes, intracellular and serum cytokine profiles.
2. Description of the Statistical Methods to Be Employed:
    - Spearman correlation of GC responsiveness and percent change in eosinophil from baseline to 4 and 24 hours, with confidence intervals and testing whether it is different from zero.
    - Model building as described in section “Description of the Analyses” (Section 6.1).
  3. Level of Significance to be Used: Two-sided 0.05
  4. Exploratory Analyses: See section 6.1 for primary objective. Similar model building strategies will be used for secondary endpoints and exploratory endpoints.

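### The fallback model and the secondary and exploratory groupings cut an already ordered prednisone dose into three classes; those association analyses should use the ordered dose

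*Combined protocol and SAP*

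**What the plan says.** The primary response is a dose: the lowest prednisone dose that controls eosinophils and symptoms, with rules for subjects who cannot taper or do not respond (Section 3.5.1). Section 3.4 sets the ladder on which it is reached: weekly 5 mg steps from 30 mg to 15 mg, then 2.5 mg steps to a 5 mg floor, with 10 mg steps from 60 mg to 30 mg for subjects who need the higher start.

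Section 6.1 sets out modelling in three stages. Linear models on the dose come first, then transformations of the dose. If neither fits, "then we will consider a cumulative logit model where we partition the GC responsiveness into 3 ordered categories". The classes are below 15 mg, 16 to 40 mg, and above 41 mg. The gatekeeping association test is a Spearman correlation on the dose itself (Sections 6.1 and 6.3), and the interim model in Section 6.4 also uses the final dose.

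Beyond the primary analysis, the classes carry more weight. Section 3.5.2 makes the three-way classification the secondary endpoint. Section 6.3 lists "Classification of subjects by GC response for assessment of clinical factors associated with GC responsiveness". Section 3.5.3 explores mechanisms "by dividing subjects into response categories for the following assessment in all subjects". Section 6.3 also says that secondary and exploratory endpoints will be modelled in a way similar to the primary objective, and that strategy begins with the dose.

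**The concern.** A cumulative logit model is built for ordered outcomes and does not need them grouped. It removes the reliance on normal errors, which is the problem that triggers the fallback, and it does so equally well on the taper doses as recorded. Grouping them first makes a 5 mg subject and a 12.5 mg subject identical, although Section 1.1 gives prediction of the maintenance dose as one reason for the study.

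The same information is lost wherever clinical factors or laboratory markers are compared across classes. The sample is capped at 40 and cannot be enlarged to compensate. Section 6.1 assumes that a sample large enough for the Spearman test is also large enough to explore the models. No power is given for any three-class analysis, and that is where the assumption is weakest.

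**Working it through.** **Inputs.** Test level: "Level of Significance to be Used: Two-sided 0.05" (Section 6.3). Correlation 0.5 under bivariate normality, and the planned size: "at the two-sided 0.05 level with 80% power is about 32 subjects" (Section 6.2). Expected enrolment is 30 to 40 (Section 6.2). Class limits are from Section 6.1 and dose steps from Section 3.4. The share of subjects in each class is not in the documents and is assumed throughout.

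**Step 1: the plan's own figures.**

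- Pearson, by Fisher's z: n = ((1.960 + 0.842) / atanh(0.5))² + 3 = (2.802 / 0.5493)² + 3 = 29.0. The plan "gives a sample size of 29 for the same situation".
- Spearman at n = 32, from 20,000 simulated data sets: 80.1%. The plan reports that "the Spearman coefficient is significantly different from zero 79.5% of the time".

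Both figures reproduce. Both concern the uncollapsed outcome.

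**Step 2: a continuous outcome cut into three ordered classes.** Tie-corrected Spearman test, correlation 0.5. Uncollapsed power is 80.1% at n = 32 and 88.7% at n = 40.

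| Assumed class shares (%) | n = 32 | Loss (points) | n = 40 | Loss (points) |
|---|---|---|---|---|
| 33/33/33 | 72.9% | 7 | 82.2% | 6.5 |
| 50/30/20 | 70.0% | 10 | 80.0% | 9 |
| 60/25/15 | 66.4% | 14 | 76.4% | 12 |
| 70/20/10 | 60.7% | 20 | 70.2% | 18.5 |
| 80/15/5 | 50.6% | 30 | 60.5% | 28 |

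More lopsided splits lose more: at 85/10/5 the loss is 36 points at either size. If the classes were compared as unordered groups (Kruskal-Wallis), the loss at n = 32 runs from 20 points at equal thirds to 44 at 80/15/5.

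**Step 3: the fairer comparison, taper ladder against three classes.** The recorded dose already has ties and a floor, so a continuous outcome flatters the alternative. I used a ladder of 5, 7.5, 10, 12.5, 15, 20, 25, 30, 40, 50 and 60 mg plus non-response, with 15 mg placed in the lowest class. Spearman test, n = 32:

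| Assumed ladder | Class shares (%) | Ladder | Classes | Loss (points) |
|---|---|---|---|---|
| Equal steps | 42/33/25 | 79.9% | 71.8% | 8 |
| Skewed | 61/27/12 | 78.5% | 65.7% | 13 |
| Half at 5 mg | 75/18/7 | 72.3% | 55.9% | 16 |
| 70% at 5 mg | 85/10/5 | 61.4% | 43.8% | 18 |

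A second set drew log-normal doses (SD of log dose 0.8, medians from 7 to 20 mg), rounded up to the taper grid with a 5 mg floor, 8,000 replicates each:

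| Class shares (%) | n = 32: ladder, classes, loss | n = 40: ladder, classes, loss |
|---|---|---|
| 36/45/19 | 79%, 73%, 6 | 88%, 83%, 5 |
| 61/32/7 | 80%, 65%, 15 | 88%, 76%, 12 |
| 83/16/1 | 77%, 46%, 31 | 86%, 56%, 30 |

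The loss is smallest with balanced classes. It is largest when few subjects end above 15 mg and the rest are spread between 5 and 15 mg.

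**Step 4: the cumulative logit model itself.** Likelihood ratio test, n = 32, 300 runs (simulation error about 2 to 3 points): skewed ladder about 85% ungrouped against 74% in three classes; half at the floor about 77% against 64%. The loss is therefore not an artefact of using Spearman as a stand-in. These figures should be compared with each other, not with the 80.1% above.

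**Step 5: how readily the fallback would be reached.** In the log-normal settings, after a log transform of the dose, a Shapiro-Wilk test rejected normal residuals in about 3 to 16% of data sets for medians of 10 to 20 mg, and in about 32 to 41% at a median of 7 mg.

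**The case against.** The strongest reply is that the planned primary inference never touches the classes. The significance test is Spearman on the dose, the 80% power refers to that test, and linear models and transformations come before the fallback. Section 6.1.2 has the model built whatever the test shows, so no significance test on three classes is planned for the primary objective. All of this stands. For the fallback, the power figures only gauge how much information the cut discards. Step 5 also shows that the fallback need not be common: in most of the settings tried, a log transform would usually suffice.

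The classes also have a purpose. Section 2.2 sets out to define a group of non-responders or suboptimal responders for mechanistic study. That stands too, so a reader who inferred that the classes bring no benefit, or should be reduced to description, would go too far.

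The top of the dose scale is not cleanly ordered. Non-responders are scored at their weight-based challenge dose, so a 50 kg non-responder (1 mg/kg × 50 kg = 50 mg) ranks below a responder held at 60 mg. The class above 41 mg absorbs this. An ungrouped model must deal with it explicitly, and doing so must not rewrite the primary endpoint.

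Finally, Section 6.3 may already permit dose-based secondary models. That is fair, but it sits uneasily with the class-based wording in 3.5.2, 3.5.3 and the same section, so the choice is left open.

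**Conclusion.** The concern holds for the conditional fallback and for the secondary and exploratory associations. Grouping is unnecessary for a cumulative logit model. At a correlation of 0.5 and 32 to 40 subjects, an association test on three classes has roughly 5 to 30 points less power than one on the ordered dose. The figure depends on assumed class shares and on placing 15 mg in the lowest class. Shares more extreme than those tried, or an unordered comparison, could exceed it.

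Three stronger readings are not supported:

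- That the primary analysis is underpowered. The lead test, the first-choice models and the interim analysis all use the uncollapsed dose.
- That the fallback will probably be used. It comes third, after transformations.
- That the response rate above 85% in Section 1.1 shows the classes will be badly unbalanced. That figure is complete or partial response at one month in a retrospective series, not a share of subjects below any dose cut.

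This is a worthwhile improvement to an exploratory part of the plan, not a threat to its main test.

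**What to change.** **Section 6.1.** Fit the fallback cumulative logit to the ordered final doses without grouping. For this ordinal analysis only, place subjects whose outcome is scored as their challenge dose in one highest category. Leave the endpoint definition in Section 3.5.1 unchanged.

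**Sections 3.5.2, 3.5.3 and 6.3.** State that associations with clinical factors and mechanistic markers use the ordered dose as the response, by rank correlation or the same ordinal model. Keep the three classes for the secondary objective of identifying the resistant or suboptimal group, for selecting samples and for description. This also settles the tension within 6.3.

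**While editing.** The class limits leave a final dose of exactly 15 mg, which is a taper step, without a class, along with doses between 15 and 16 mg and from above 40 up to 41 mg. The class names also differ between Sections 3.5.2 and 6.1. These passages must be reconciled.

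**Cost.** Analysis wording only: no new data, and standard software fits the model. The ungrouped model has more intercepts and leans on proportional odds across more levels, so that assumption should be examined. Results should also be summarised by class for clinical readers.

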### **6.1.1. Appropriate Methods and Timing for Analyzing Outcome Measures**

Outcome measures will be measured using weekly or bi-weekly eosinophil count assessments at the subject's home physician office. Outcome measures will be assessed once 30% of subjects have been enrolled and challenged, and again at completion of the final subject enrollment.

### **6.1.2. Addressing Study Objectives**

Although the primary objective is an exploratory model building, we do consider the simple null hypothesis that there is no correlation between % change in eosinophil count at 4 and 24 hours after challenge and GC response. Regardless of whether that test is significant or not, we will attempt to predict the GC response through the model building strategy described in the Section 6.1 on Description of the Analyses.

## 6.2. Sample Size Justification

The sample size of this study is practically limited by the number of subjects available for study. Currently, about 30-35 new hypereosinophilic subjects per year are seen at the NIH and enrolled on protocol 94-I-0079, of which approximately 10% would meet inclusion criteria for this protocol. Consequently, we expect that we can enroll 30-40 subjects in this study over a 13-year period.

To show that this number of subjects is not unreasonably small, we calculate the sample size for a Spearman's correlation coefficient. If true correlation is 0.5 between a predictor variable (ERR at 4 or 24 hours) and the GC responsiveness (see Description of the Study, Section 3.1), the total number of subjects needed to show that the correlation is different from zero at the two-sided 0.05 level with 80% power is about 32 subjects. We calculated this by simulating 10,000 data sets of 32 bivariate random normal variables with correlation 0.5 and seeing that the Spearman coefficient is significantly different from zero 79.5% of the time. This is similar to the usual sample size calculation for Pearson's correlation(17) or (18) that gives a sample size of 29 for the same situation.

Because the predictor and outcome variables are both continuous, if the true change in the dependent variables is 0.5 standard deviations per 1 standard deviation change in the independent variable, a clinically important measurement of association between response to a steroid challenge and final required dose of GC will be possible.

## 6.3. Final Analysis Plan

### 1. Study Endpoints:

- Primary: GC responsiveness.
  - Definition: See primary endpoint for definition of GC responsiveness.
  - Validity and Reliability: This is a rare disease, and standard care for this disease is still being developed. There is no standard endpoint, and this endpoint has not been used before. One of the purposes of this study is to see if this endpoint can be reliably predicted. The endpoint has face validity because the dose that controls eosinophil concentration is useful for determining the extent of a subject's disease and their responsiveness to steroid therapy. We will first try and predict GC responsiveness as described in section "Description of the Analyses" (Section 6.1), but may also try to predict the categorization of the GC responsiveness into 3 ordered categories described in section "Description of the Analyses".
  - Predictor Variables: All predictor variables will be measured in the first 24 hours after initial dose, and will be blinded to the PI and Accountable Physician. These variables will be used to predict the GC responsiveness:

percent change in eosinophil count from baseline to 4 and 24 hours and steroid absorption.

- Secondary:
    - Classification of subjects by GC response for assessment of clinical factors associated with GC responsiveness (including HES variant, pattern of organ involvement and laboratory parameters)
  - Exploratory
    - Exploratory analyses of potential mechanisms and in vitro correlates of GC resistance, including impaired steroid absorption, cell surface markers on lymphocytes, intracellular and serum cytokine profiles.
2. Description of the Statistical Methods to Be Employed:
    - Spearman correlation of GC responsiveness and percent change in eosinophil from baseline to 4 and 24 hours, with confidence intervals and testing whether it is different from zero.
    - Model building as described in section “Description of the Analyses” (Section 6.1).
  3. Level of Significance to be Used: Two-sided 0.05
  4. Exploratory Analyses: See section 6.1 for primary objective. Similar model building strategies will be used for secondary endpoints and exploratory endpoints.
  5. Handling of Missing and Spurious Data: We have defined the primary endpoint so that there should be little missing data. For example, subjects that are unable to control their eosinophil counts with 30-60 mg prednisone will still have a defined endpoint and their results will be included in the analysis. Based on prior experience with this subject cohort, we anticipate an extremely low dropout rate (<5%/year).

#### **6.4. Interim Analysis Plan**

Due to the rare nature of the disease, various investigators have asked whether an interim analysis would be appropriate in this rare population. Since approximately two thirds of the projected subjects have completed the study, we are able to perform an interim analysis using ERR to predict GC responsiveness. Although this is an additional analysis, since the original final analysis plan allowed for an unspecified number of different models, this does not change the overall analysis plan in any substantial way. Nevertheless, trying many models may result in an overfit final result, therefore, for the interim analysis we will try only one flexible model.

We use a linear model to predict the GC responsiveness using either a first, second or third order polynomial of log(ERR) at 4 hours in the model and the final end-prednisone dose of each subject as the GC response as defined in section 3.5.1. The choice between the three models will be made by the one with minimum AIC (Akiake

information criteria). To evaluate the prediction, we will use a leave-one-out cross validated estimate of R squared, where for each fit with a point left out we use the minimum AIC model of the three. Because the entire model finding procedure is cross validated, the estimate of R squared will not be biased upward by using the lowest AIC from the three models. As in the final analysis plan, to test for significance between log(ERR) and GC responsiveness, we test whether the Spearman (i.e., rank) correlation is significantly different from zero, and calculate estimates and associated confidence intervals for Spearman's correlation.

If the interim model appears to explain the variation of the GC responsiveness (i.e., has a large cross validated R squared), then we can use the interim model to predict the GC responsiveness of the subsequent subjects that enter the study as a validation cohort. Because we expect few additional subjects (<15), our validation would only be able to detect extreme departures from the model. We test for extreme departures from the model by creating a 95% prediction interval and testing whether we can show that significantly less than 95% of the subsequent subjects fall within that prediction interval. For all sample sizes 5 or greater, we have at least 80% power to show that the model fails (the 95% prediction interval covers less than 95% of subsequent responses) if the true proportion that fall within the 95% prediction interval is 50% or less. It is possible that the prediction intervals from the model are so wide that they will not be clinically useful, perhaps as a result of insufficient subjects enrolled, in which case the study will continue since the secondary and exploratory outcomes of the study will continue to be useful for studies of GC effects on eosinophils.

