### 3.4. Procedures and Laboratory Testing

Subjects will receive a single dose of prednisone prescribed by the PI or designee to be taken by mouth at a dose of 1 mg/kg (rounded to the nearest 5 mg) between the hours of 7:30 and 9am on the day of study. Laboratory testing, including a baseline cortisol level, CBC with differential, and research specimens (see Appendix B) will be drawn prior to prednisone administration and at 2, 4 and 24 hours after prednisone administration. Investigators will be blinded to the 2-hour, 4-hour and 24-hour eosinophil counts (the results will not appear in the NIH Clinical Research Information System (CRIS), but will be available from the Clinical Pathology internal system for analysis once the trial is completed). All blood draws will be timed and will occur in outpatient phlebotomy, outpatient clinic or inpatient unit that is able to draw at specific times to prevent variability in draw times across the subject cohorts.

In normal subjects, prednisone is rapidly absorbed and metabolized with peak levels at 2-4 hours and a biologic half-life of 12-36 hours. Serum will be stored from blood drawn at the 4-hour time point for assessment of synthetic glucocorticoid levels, including prednisone and its metabolite prednisolone. Subjects may be asked to undergo further workup for causes of poor absorption by their home physician or at NIH if indicated.

After the 24-hour challenge, subjects will be started on a GC taper to determine the lowest dose of GC that is able to suppress signs and symptoms of HES and maintain the peripheral eosinophil count below 1000/ $\mu$ l. GC will be initiated at 30 mg in all subjects, and the taper will proceed according to an algorithm (Appendix E). GC will be tapered by 5 mg weekly until a dose of 15 mg is reached. The dose will then be tapered by 2.5 mg weekly until a dose of 5 mg is reached or the eosinophil count rises.

In some cases, an initial starting dose of 30 mg of prednisone will be insufficient to control eosinophilia. If AEC is  $>1000/\mu$ L 1 week after the initiation of GC, the GC dose will be increased to 60 mg and a taper initiated from this higher dose. A CBC with

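### The interim analysis repeats the 4 h Spearman test, but the plan does not say which look carries the two-sided 0.05; at 0.05 each time, the overall false-positive rate is about 8%.

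*Combined protocol and SAP*

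**What the plan says.** Section 6.3, item 2, plans a test against zero at the final analysis: "Spearman correlation of GC responsiveness and percent change in eosinophil from baseline to 4 and 24 hours, with confidence intervals and testing whether it is" (the sentence is cut here). Item 3 gives the only level: "Level of Significance to be Used: Two-sided 0.05".

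Section 6.4 adds an interim analysis: "Since approximately two thirds of the projected subjects have completed the study, we are able to perform an interim analysis". Its model uses ERR at 4 hours only ("second or third order polynomial of log(ERR) at 4 hours in the model", or a straight line). The section takes its significance test over from the final plan ("As in the final analysis plan, to test for significance between log(ERR) and GC responsiveness"). The hypothesis is again that there is no rank correlation: "we test whether the Spearman (i.e., rank) correlation is significantly different from zero". It gives no interim level and no spending rule, and does not call the interim p-value descriptive. It defends the extra analysis on the ground that the final plan already left the number of models open.

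Section 6.1.1 separately says: "Outcome measures will be assessed once 30% of subjects have been enrolled and challenged, and again at completion of the final subject enrollment". It names no test there.

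Section 3.4 keeps the post-challenge eosinophil counts from the investigators, "but will be available from the Clinical Pathology internal system for analysis once the trial is completed".

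**The concern.** A test at 0.05 on two thirds of the data and again on all of it gives two chances of a false positive. The sample size in 6.2 is built on a single two-sided 0.05 test, and no section says which look that level belongs to.

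Section 6.1 introduces the Spearman test as a check that the final model is not fitted to noise, and 6.1.2 lets modelling proceed whatever the test shows. What the test contributes is therefore its error rate, so that rate should be the stated one.

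The defence in 6.4 does not reach this. It concerns how many models are tried, and leave-one-out cross-validation protects the R squared estimate. Neither affects a hypothesis test repeated on accumulating data. Taking the log of ERR does not make it a different test either, because ranks are unchanged by an increasing transformation wherever the log is defined.

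**Working it through.** **Inputs.** Two-sided 0.05 (6.3). True correlation 0.5, 32 subjects, simulated power 79.5%, Pearson sample size 29, expected enrolment 30-40 (6.2). Interim at about two thirds (6.4), so about 20 of 30, 21 of 32 or 27 of 40. Assumption: the interim test is also at 0.05, since 6.4 points to the final plan and gives no other level.

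**1. The plan's own figures.**
- Pearson: N = ((1.960 + 0.842) / atanh(0.5))² + 3 = 29.0, against 29 stated.
- Spearman power at n = 32 and correlation 0.5, by simulation: 80.0%, against 79.5% stated.

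Both reproduce, as single-test figures.

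**2. Two looks, normal theory.** With no association, the two test statistics have correlation √(2/3) = 0.816. The overall error is 1 − P(|Z1| < 1.96 and |Z2| < 1.96) = 1 − 0.923 = 7.7%.

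**3. Two looks, direct simulation of the Spearman test.** No association, 4 h only, t-approximation p-values, 400,000 data sets per N:

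| N | Looks | Either look p < 0.05 | Final alone | 0.001 interim, 0.05 final |
|---|---|---|---|---|
| 30 | 20, 30 | 8.0% | 5.1% | 5.1% |
| 32 | 21, 32 | 8.0% | 5.1% | 5.1% |
| 40 | 27, 40 | 7.9% | 5.0% | 5.1% |

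Across repeated runs the two-look figure lies between 7.8% and 8.2%. With no true association, 56-58% of significant interim results are no longer significant at the end, so an interim claim could be contradicted by the study's own final test.

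**4. Other ways to hold the level.** O'Brien-Fleming-type spending gives nominal two-sided levels of 0.0121 at two thirds and 0.0463 at the end (5.0% in normal theory). The power of the final test at n = 32 then falls from about 80.1% to 79.2%. A constant level of about 0.032 at each look also gives 5% in normal theory. With 0.001 at the interim, the final test stays at 0.05 and its power does not change.

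**5. The 30% assessment, only if it included the test.** With 0.05 at 30%, two thirds and the end, the total would be about 11.5-12.5%. Section 6.1.1 does not say that the test is run then.

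**The case against.** The strongest reply is that nothing depends on the interim p-value. Section 6.1 calls the primary objective exploratory. Modelling proceeds whatever the test shows (6.1.2), use of the interim model depends on a large cross-validated R squared (6.4), and no stopping or success rule refers to the Spearman test. The final 4 h test taken alone keeps its 5%, and the 0.05 at the interim is inferred. All of this stands. It lowers the severity but does not supply the missing statement of which look carries the level.

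A reader might infer more than the documents support:

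- **That three tests are planned, for an error of 11.5% or more.** Section 6.1.1 names neither ERR nor a test at 30%. It ties outcome measures to eosinophil counts taken at the home physician's office, and 3.4 does not blind investigators to the counts obtained during the taper. For the same reason, it does not show that blinded challenge counts are opened at 30%.
- **That the Spearman test is the only safeguard against a model of noise.** Section 6.4 also limits the interim to one flexible model, cross-validates the whole selection procedure, and plans a validation cohort with a test of prediction-interval coverage. By the plan's own account that validation can detect only extreme departures, but it exists.
- **That a significant interim result would be reported as proof that the challenge predicts dose.** No section says so.

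**Conclusion.** The point holds for the two looks at the 4 h correlation. Read as 0.05 at each, the chance of a false significant result at either look is about 8% (7.7% in normal theory, 7.8-8.2% in simulation for N = 30-40). This assumes the interim level is 0.05, the interim falls at about two thirds, and ERR and its log rank the subjects alike.

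Severity is moderate to low. The gap is an unstated allocation of the level in an exploratory test on which no decision rests.

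Two matters lie outside this figure. The 24 h correlation is tested only at the end. Testing 4 h and 24 h together at 0.05 there gives 7.3-10.0% for an assumed correlation between the two predictors from 0.9 down to 0. That is a separate multiplicity. The wording on blinded counts is not an error-rate matter, but as written 3.4 does not allow the interim that 6.4 describes.

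**What to change.** - **6.4:** report the interim Spearman correlation as an estimate with a confidence interval and make no significance claim. Alternatively, test it at two-sided 0.001, which keeps the 4 h total at about 5%.
- **6.3, item 3:** state that the two-sided 0.05 for the 4 h correlation applies at the final analysis only. Do not describe it as the single final test, because 24 h is tested as well; this change does not resolve the 4 h and 24 h multiplicity.
- **6.1.1:** state that the 30% assessment includes no test of ERR against GC responsiveness.
- **3.4 and 6.4:** reconcile the release of blinded counts at trial completion with an interim that uses subjects who have completed the study.

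The cost is a few sentences, with no change to data collection or to the power of the final test. The one loss is that an interim p-value between 0.001 and 0.05 can no longer be called significant.
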